6 STUDY DESIGN AND PROCEDURES

- Study design
 - The study will use a difference-in-differences design in which changes before and after the intervention will be compared between a treatment group and a control group.
 - The treatment group will include all patients undergoing tonsillectomy at C.S. Mott Hospital by a pediatric otolaryngology faculty member at the University of Michigan.
 - The control group will include all patients undergoing tonsillectomy at University Hospital, Brighton Center for Specialty Care, or Livonia Center for Specialty Care by a general otolaryngology faculty member at the University of Michigan.
- Data collection procedures throughout the study
 - There will be three sets of surveys: a baseline survey, daily surveys on post-operative days 1-13, and a final survey on post-operative day 14. Post-operative surveys will be sent to all patients who enroll, including those who are not prescribed opioids post-operatively. These patients will not be included in the primary or secondary analysis but will be analyzed in a separate study examining pain recovery without opioids.
 - Baseline survey: Patients will be asked to complete a 10-15 minute survey assessing demographics, reason for tonsillectomy, current pain, chronic pain, history of opioid use, history of opioid misuse, family chronic opioid use, depression, substance use disorders, anxiety, sleep, and global health. Patients will be e-mailed a link to the baseline survey upon enrollment; for patients who cannot receive e-mail links, the survey will be administered over the phone. For patients at Mott or University Hospital recruited in-person, the baseline survey will be administered by a study team member in-person through Qualtrics on a tablet. Patients sent the baseline survey who do not complete it before surgery will be contacted via e-mail or by phone to remind them or approached in-person to complete it through Qualtrics on a tablet. If patients are contacted by phone, they will be given the option to complete the survey over the phone.

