10 STATISTICAL CONSIDERATIONS

- Outcomes in primary analysis
 - Number of doses in the discharge opioid prescription
 - Proportion of patients in which the number of doses in the discharge opioid prescription equals the number of doses in the new default settings
 - Proportion of patients prescribed opioids at discharge
 - Proportion of patients prescribed opioids at discharge who had at least one opioid prescription refill from UM during the two weeks after surgery
 - Proportion of patients who saw a UM provider in an office due to pain during the two weeks after surgery

- Proportion of patients with at least one emergency department visit or hospitalization at UM for pain during the two weeks after surgery
- Additional outcomes in secondary analysis (based on data from the final post-operative day 14 survey)
 - Overall satisfaction with pain control during the two weeks after surgery (scale of 1-10)
 - Proportion of patients who reported that their pain was well-controlled
 - Proportion of patients whose overall pain control was rated as much worse or worse than expected
 - Proportion of patients whose pain has resolved by day 14 after surgery
 - Pain score over the past 7 days at its worst (scale of 0-10)
 - Pain score over the past 7 days on average (scale of 0-10)
 - Number of opioid doses taken during the two weeks after surgery
 - Proportion of patients with leftover doses of opioids
 - Proportion of patients with leftover doses who disposed of them
 - Proportion of patients who misused opioids belonging to others at least once during the two weeks after surgery
 - Proportion of patients who misused their own opioids at least once during the two weeks after surgery
 - PHQ-8 score (depression)
 - Score on PROMIS Pediatric Anxiety – Short Form 8a
 - Score on PROMIS Sleep Disturbance – Short Form 8a
 - Proportion of patients who saw their primary care provider (or a colleague) in the office due to poorly controlled pain at least once during the two weeks after surgery
 - Proportion of patients who visited an urgent care center due to poorly controlled pain at least once during the two weeks after surgery
 - Proportion of patients who visited a retail clinic due to poorly controlled pain at least once during the two weeks after surgery
 - Proportion of patients who went to an emergency department and/or were hospitalized due to poorly controlled pain at least once during the two weeks after surgery

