- Data from the daily surveys will be used to assess whether daily opioid consumption reports matches the consumption reported on the final post-operative day 14, and will also be analyzed in a separate study assessing the trajectory of pain and opioid use after tonsillectomy.
- We will fit linear or logistic regression models assessing outcomes as a function of an indicator of post-intervention status, an indicator of treatment group status, and its interaction, controlling for covariates such as demographics (e.g., age, sex) and baseline co-morbidities (e.g., depression, anxiety). We will graphically and statistically assess the comparability of pre-intervention monthly trends in outcomes between the treatment and control groups.

- We hypothesize that there will be no change in outcomes in the control group (i.e., that the post-intervention trend in outcomes in the control group will be an extension of the pre-intervention trend in outcomes). In contrast, we hypothesize that the number of doses and opioid consumption will drop in the treatment group after the intervention; that the proportion of patients with prescriptions concordant with the new defaults will increase after the intervention; and that there will be no change in balancing measures such as pain control or depression.
- Sensitivity analyses
 - Statistical modeling: we will explore whether results change when replacing the indicator of treatment group status with a vector of fixed effects for the prescribing clinician, and will explore the feasibility of using an interrupted time series approach instead of a difference-in-differences approach.
 - We will determine whether any otolaryngology residents wrote opioid prescriptions for both a pediatric otolaryngology and general otolaryngology patients in the post-intervention period, and exclude data from any such residents from the analysis
 - We will exclude opioid prescriptions written for patients of the chief of pediatric otolaryngology, who will be involved in setting the new defaults
- Subgroup analysis will occur by age group (ages 12-17 years vs 18 and older), gender, payer type (private/public), and baseline co-morbidities (e.g., depression and anxiety).
- We will separately analyze data from pediatric otolaryngology patients undergoing surgery outside of Mott and general otolaryngology patients undergoing surgery at Mott to assess for any spillover effects.

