 - In the baseline and post-operative day 14 surveys, we will administer the PHQ-8, a depression screen that does not contain any questions regarding self-harm. These surveys will predominantly be administered via a tablet or online Qualtrics survey. A small number of patients may be administered the surveys on the phone (e.g., if they cannot receive e-mail links to online surveys). If, in the course of these phone surveys, a patient discloses thoughts of self-harm to the study coordinator, the study coordinator will contact a mental health professional on the team, who will contact patients and screen for suicide risk using a suicidal ideation protocol developed by the University of Michigan Back and Pain Center. Patients without an imminent threat of self-harm will be referred to mental health services. For patients with an imminent threat of self-harm, we will follow the protocol by trying to keep them on the phone while paging an emergency University of Michigan-based pager. Details of the protocol are included in the data and safety monitoring plan. If the patient with imminent threat

of self-harm is a minor, we will additionally inform their parents or guardians.

- Trial Stopping Rules
 - The trial will be stopped if it is discovered that the intervention has resulted in substantially higher rates of uncontrolled pain, depression, or opioid misuse. This is felt to be unlikely for the reasons articulated in Section 3.

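### The sleep, anxiety and depression models are not pre-specified to adjust for the patient's own baseline score; sleep is the clearest gap, and the likely cost is precision

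*Combined protocol and SAP*

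**What the plan says.** Section 10 (Statistical Considerations) puts the three scales under the lead-in "Additional outcomes in secondary analysis (based on data from the final post-operative day 14 survey"). They are "PHQ-8 score (depression"), "Score on PROMIS Pediatric Anxiety – Short Form 8a" and "Score on PROMIS Sleep Disturbance – Short Form 8a". No change from baseline is defined for any of them.

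The baseline survey in section 6 covers, among other domains, "depression, substance use disorders, anxiety, sleep, and global health", and also the reason for tonsillectomy. Section 6 does not name the instruments. Section 11.3 does so for depression only: "In the baseline and post-operative day 14 surveys, we will administer the PHQ-8".

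Section 4 excludes from the survey-based analysis anyone who did not complete both the baseline and the day-14 survey.

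One model statement in section 10 serves every outcome. It is a linear or logistic regression on period, group and their interaction, "controlling for covariates such as demographics (e.g., age, sex) and baseline co-morbidities (e.g., depression, anxiety"). The same section reuses baseline co-morbidities, again with depression and anxiety as examples, as a subgroup factor beside age group, gender and payer type.

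**The concern.** For each of these scales, the patient's own score before surgery is an obvious candidate to predict the score at day 14. It is collected, and by the eligibility rule every analysed patient has completed the survey that holds it. The plan does not commit to using it. Baseline sleep is not mentioned in the model at all. Depression and anxiety are mentioned, but as co-morbidities. Their use as a subgroup factor suggests categories more than continuous scores, although the form is not stated.

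The stakes lie in how these outcomes will be read. Section 1 lists worse sleep, anxiety and depression among the unintended consequences to be assessed. Section 10 hypothesises no change in balancing measures, with depression as an example, and section 11.3 includes depression in the stopping rule. A finding of no change is only as informative as its interval is narrow, and the survey sample is small. The periods also contain different patients, so if the baseline mix moved differently in the two groups, an unadjusted model would carry part of that movement into the estimate.

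**Working it through.** **Inputs from the documents.** Section 10 gives 113 treatment and 85 control patients, 65% consent, and hence 74 and 55 survey patients (129 in all). Section 6 gives 10 usable pre-intervention months (12 less April and May 2020) and 10 post-intervention months.

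**Assumptions.** The documents give no SD, significance level or baseline-to-day-14 correlation for these scales. I assume an even split by period, equal SDs in all cells and at both times, independent patients, a 95% interval, and a correlation r of 0.3, 0.5 or 0.7.

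**Step 1: the plan's own figure.** 113 × 0.65 = 73.45, 85 × 0.65 = 55.25 and 198 × 0.65 = 128.7. The stated 74, 55 and 129 reproduce to within rounding.

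**Step 2: precision without baseline adjustment.** The cells are 37, 37, 27.5 and 27.5. In SD units,

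SE = √(1/37 + 1/37 + 1/27.5 + 1/27.5) = √(4/74 + 4/55) = 0.356

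95% half-width = 1.96 × 0.356 = 0.698, about 0.70 SD.

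The split matters little: at 40/60 the SE is 0.363 and the half-width 1.96 × 0.363 = 0.71 SD.

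**Step 3: precision with the own-baseline score as a covariate.** The SE is multiplied by √(1 − r²), and the equivalent gain in sample size is 1/(1 − r²).

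| r (assumed) | √(1 − r²) | SE (SD) | Half-width (SD) | Equivalent total N |
|---|---|---|---|---|
| none | 1.000 | 0.356 | 0.70 | 129 |
| 0.3 | 0.954 | 0.340 | 0.67 | 129 × 1.10 ≈ 142 |
| 0.5 | 0.866 | 0.308 | 0.60 | 129 × 1.33 ≈ 172 |
| 0.7 | 0.714 | 0.254 | 0.50 | 129 × 1.96 ≈ 253 |

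The first row is a model with no covariates. The plan's model has some, so the table bounds the gain from above. It fits sleep best, since baseline sleep is not named. For depression and anxiety, some of the gain may already be captured.

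**Step 4: is the day-14 score itself the problem?** No. A change score would multiply the SE by √(2(1 − r)), which is 1.18, 1.00 and 0.77 at r = 0.3, 0.5 and 0.7. The adjusted day-14 score (0.95, 0.87, 0.71) is better at each value.

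**Step 5: bias.** A baseline shift common to both groups cancels in the interaction term. If the shift differs between groups by d SD, the unadjusted estimate is off by r × d, because the slope equals r when the SDs are equal. With d = 0.2 (assumed), that is 0.06, 0.10 or 0.14 SD.

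**The case against.** The strongest reply is that the plan already allows this adjustment. The covariates are given as examples, so baseline sleep and reason for tonsillectomy are not ruled out. Baseline depression and anxiety are named, and the PHQ-8 is given at both times. A reader might infer that none of the three scales is tied to baseline, or that depression and anxiety will enter only as yes/no conditions. The documents support neither: the form is simply unstated. What remains is that an open list does not commit the analysts to the adjustment and leaves the covariates to be chosen after the data are seen. Sleep is not named under any reading.

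A reader might also infer that any change in patient mix between periods, such as one following the pandemic, will be read as an effect of the new default. That overlooks the concurrent control group and the exclusion of April and May 2020. Only a differential shift biases the result. One is possible, because the groups differ by service and site, and section 5 allows in-person recruitment at Mott and University Hospital but only telephone recruitment at Brighton and Livonia. Nothing in the documents shows that it will occur.

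The gain may also be modest. At r = 0.3 it is worth about 10% more patients. Sleep disturbed by tonsil disease before surgery may predict sleep at day 14 only weakly. Even at r = 0.7 the half-width is still 0.50 SD, and these are three of 18 additional secondary outcomes. All of this stands, and it limits the size of the point. It does not remove a gain that costs nothing to take.

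Finally, it is tempting to ask the same for the 0–10 pain outcomes. Section 6 lists current pain at baseline without saying that it is a rating, and nothing in the documents shows that pain before surgery predicts pain after it. The point does not extend there.

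**Conclusion.** The point holds as a gap in specification with a concrete cost in precision. It is clear for sleep. For depression and anxiety it is partial, because baseline status is named but its form is not. Relative to a model without baseline, own-baseline adjustment narrows the 95% half-width from about 0.70 SD to 0.67, 0.60 or 0.50 SD. These figures rest on the assumed correlations, the even split and independent patients. The 74 and 55 reflect consent only, so patients who consent but do not complete both surveys would widen every interval. Bias is conditional on a differential shift in baseline mix, and its size here is illustrative. Because the outcomes are secondary, this is a change the sponsor should make, but it does not undermine the design.

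**What to change.** Add to the model paragraph in section 10 that the depression, anxiety and sleep models each include the patient's own baseline score in that domain as a continuous covariate, and name sleep explicitly. For depression this is the baseline PHQ-8. For anxiety and sleep it is the measure used in the baseline survey, on the same PROMIS form if that form was given then; the plan should state which instrument was used. Keep the day-14 score as the outcome. Reason for tonsillectomy may be added to the sleep model.

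The cost is a sentence or two in the plan. The baseline survey already covers these domains and is already required for the secondary analysis, so no data are added and no patients are lost beyond those with unanswered baseline items.

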- Daily surveys: At 12:01 am on post-operative days 1 through 13, patients will be e-mailed a daily link to complete a 1-minute online Qualtrics survey in which pain and opioid consumption over the prior 24 hours will be assessed. The post-operative day 7 survey will be similar except that it will include additional questions assessing pain over the prior 7 days. Patients who cannot receive e-mail links will not be sent daily surveys. E-mail or telephone follow-up will not occur for the daily surveys on post-operative days 1-13.
 - Final survey: on post-operative day 14, patients will be e-mailed a link to complete a 10-15-minute online Qualtrics survey assessing pain control, opioid use, opioid disposal, opioid misuse, acetaminophen/ibuprofen use, depression, anxiety, sleep, and health care utilization during the 14 days after surgery, including refills and visits to the emergency department or primary care for pain. Patients who cannot receive e-mail links will be called and the survey will be administered over the phone. Patients may be contacted via e-mail or by phone to remind them to complete surveys. If patients are contacted by phone, they will be given the option to complete the survey over the phone.
 - DataDirect and MiChart will be queried to determine opioid use prior to the day of surgery based on the admission history and physical, patient demographics, the dosing parameters of post-operative opioid prescriptions, the number of return visits for pain at the University of Michigan in the 14 days after surgery, and the number of opioid refills in the 14 days after surgery.
- Timeline
 - The pre-intervention period will start on October 1, 2019 and end September 30, 2020; the months of April and May 2020 will be excluded as elective surgeries were scaled down owing to the COVID-19 pandemic. The intervention will be implemented on October 1, 2020. The post-intervention period will start October 1, 2020 and end on July 31, 2021.
 - Nature of intervention
 - Currently, pediatric otolaryngology attendings and their residents use a MiChart tonsillectomy orderset with three options: patients < 12 years, patients ≥12 years, and M-POP. Under the orderset for patients ≥12 years, the default is currently 30 doses, consistent with the current departmental prescribing standard (see MiChart screenshot below).
 - During the pre-intervention period, no changes will be made to the default number of doses or any other dosing parameter.

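### The main model for doses prescribed states no allowance for correlation within prescribing clinicians; clustered standard errors would be a cheap improvement

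*Combined protocol and SAP*

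**What the plan says.** Section 10 (Statistical Considerations) gives the main model in one sentence: "We will fit linear or logistic regression models assessing outcomes as a function of an indicator of post-intervention status", together with a treatment-group indicator, the interaction of the two, and patient covariates such as age, sex, depression and anxiety. No robust or clustered standard error, random effect or GEE is stated there or elsewhere.

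The only clinician-level modelling is a sensitivity analysis that will explore "replacing the indicator of treatment group status with a vector of fixed effects for the prescribing clinician". Two further checks involve prescribers. One looks for whether "any otolaryngology residents wrote opioid prescriptions for both a pediatric otolaryngology and general otolaryngology patients in the post-intervention period" and drops the data of those residents. The other states: "We will exclude opioid prescriptions written for patients of the chief of pediatric otolaryngology". These address contamination and involvement in setting the default, not correlation.

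Section 6 describes who acts on the default: "pediatric otolaryngology attendings and their residents use a MiChart tonsillectomy orderset". The treatment group is "all patients undergoing tonsillectomy at C.S. Mott Hospital by a pediatric otolaryngology faculty member at the University of Michigan"; the control group is defined by other sites and the general service. On timing, "The post-intervention period will start October 1, 2020 and end on July 31, 2021"; the pre-intervention period opens in October 2019. The sample-size text gives expected patient counts only.

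**The concern.** The dose count and the match to the new default are chosen by a clinician, and one clinician's patients are likely to receive similar prescriptions. A regression that treats 198 prescriptions as independent may then overstate the information in them.

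The plan expects its effects in these outcomes: it hypothesizes a fall in doses in the treatment group and "that the proportion of patients with prescriptions concordant with the new defaults will increase after the intervention". Understated standard errors would favour those hypotheses. A large fall in doses would survive wider intervals; a modest effect, or one in a subgroup, might not.

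The fixed-effects check does not settle this. It is exploratory, so it leaves the main intervals as they are, and it removes only what is constant about a prescriber. The intervention is meant to change prescribing. If some clinicians adopt the new default more readily than others, that is variation by clinician and period, which fixed effects leave in the error term.

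**Working it through.** **The plan's own figure.** 113 + 85 = 198, as stated. There is no power calculation to reproduce.

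**Inputs from the documents.** 113 treatment and 85 control patients (section 10). The pre-intervention period is 12 months less April and May 2020, so 10 months; October 2020 to July 2021 is also 10 months (section 6). I therefore assume an even split: 56.5 and 42.5 patients per period.

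**Assumed inputs.** ICC (ρ) of 0.10 or 0.20; 6 treatment and 4 control clinicians (10 in total) or 20 and 15 (35 in total); correlation r between a clinician's effects in the two periods.

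**Step 1, independence.** In SD units the variance of the difference-in-differences is 2/56.5 + 2/42.5 = 0.0354 + 0.0471 = 0.0825, so SE = 0.287. The minimum detectable difference at two-sided 5% and 80% power is (1.96 + 0.84) × 0.287 = 0.80 SD.

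**Step 2, clinician effects.** With equal caseloads of m patients per clinician and period, each group's variance is multiplied by 1 − ρ + mρ(1 − r).
- r = 1 (same clinicians, stable habits): the factor is 1 − ρ, so ordinary standard errors are slightly conservative.
- r = 0 (equivalent to complete turnover): the factor is the usual 1 + (m − 1)ρ.
- r = 0.5 (equivalent to half the clinicians being replaced): shown in the table.

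The SE ratio is the square root of the inflated variance over 0.0825. Type I error is 2[1 − Φ(1.96/SE ratio)].

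| Clinicians | m (treatment, control) | ρ | Factors at r = 0.5 | Variance | SE ratio | Type I error |
|---|---|---|---|---|---|---|
| 6 and 4 | 9.42, 10.62 | 0.10 | 1.371, 1.431 | 0.1159 | 1.185 | 9.8% |
| 6 and 4 | 9.42, 10.62 | 0.20 | 1.742, 1.863 | 0.1493 | 1.346 | 14.5% |
| 20 and 15 | 2.83, 2.83 | 0.10 | 1.041, 1.042 | 0.0859 | 1.021 | 5.5% |
| 20 and 15 | 2.83, 2.83 | 0.20 | 1.083, 1.083 | 0.0893 | 1.041 | 6.0% |

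**Step 3, simulation of the dose outcome.** No true effect, nominal 5%. Simulation A: 2,000 runs per setting, random caseloads, ICC 0.05 to 0.20, 10 to 35 clinicians. Simulation B: 3,000 runs, 6 or 12 clinicians per group. Simulation C: 400 runs, ICC 0.10 to 0.20, 10 or 35 clinicians.

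| Scenario | Ordinary SE, A | Ordinary SE, B | Ordinary SE, C | Clinician fixed effects |
|---|---|---|---|---|
| Stable clinicians and habits | 4.1–6.7% | 4.7–5.0% (ICC 0.20) | 3.2–5.8% | 4.2–5.5% (B) |
| 50% turnover | 6.0–14.5% | 9.8–15.3% (ICC 0.20) | 5.8–21.2%, pooled with the next row | 5.0–5.5% (B) |
| Cross-period correlation 0.5 | 5.7–18.2% | not run | see row above | 5.4–19.2% (A) |
| Full turnover | 5.9–25.2% | not run | 8.8–26.0% | not estimable |

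The 21.2% rests on 400 runs and has a Monte Carlo error of about 2 points (√(0.212 × 0.788/400) = 0.020). The larger simulation tops out at 18.2%. Fixed effects restore the nominal level under partial turnover and do almost nothing when habits change.

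**Step 4, the remedy for doses.** Clinician-clustered CR2 with Satterthwaite degrees of freedom held 3.1–6.4% in simulation A; CR2 held 2.5–6.5% in C. The simpler CR1 reached 7.5% with few clinicians in B, hence the few-cluster correction.

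**Step 5, the match outcome.** With a baseline match rate of 20.6% (the pre-intervention share in the adult emergency department study cited in section 1, used only as an illustration), ordinary logistic regression rejects 5.5–11.7% at correlation 0.5 and 5.1–9.7% at 50% turnover. With a 5% rate in every cell it rejects 0.2–4.0%, and 29–50% of runs have an empty cell. The linear probability model with CR2 held 3.0–5.7%, but was run only at 20.6%.

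**The case against.** Section 10 describes a mean model and does not rule out clustered standard errors, so this is a gap in specification rather than a demonstrated error. That stands, and it is why the point is an improvement rather than a fault that invalidates the analysis.

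The size depends entirely on inputs that the documents do not give. In ordinary cases it is small: with 35 clinicians, type I error is 5.5–6.0% at correlation 0.8 and 5.6–6.5% at 25% turnover. That stands too. A reader might infer from the full-turnover rows that the true error rate is near 25%. That needs every prescriber to be replaced, few clinicians and an ICC of 0.20. Nothing in section 6 suggests complete replacement over the 22 months.

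A reader might also infer that the match outcome is inflated in the same way. The documents do not support that. Section 6 puts the existing treatment-side default at 30 doses and says that the new one will be lower, so matches before the change are plausibly rare in the treatment group. In that case ordinary logistic regression is conservative and the difficulty is sparse cells. The low-rate check used one common rate in all four cells, so it shows a direction, not a size.

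Finally, the default is assigned by site and service. Clinician clustering cannot absorb a shock shared by a whole group and period, so it does not guarantee nominal coverage. This limits the remedy but does not remove the reason for it.

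**Conclusion.** The point holds as a cheap improvement. The main model states no allowance for within-clinician correlation in the dose outcome, and the planned fixed-effects check is exploratory and partial. With stable clinicians and habits, ordinary standard errors are about right. With 50% turnover or a cross-period correlation of 0.5, type I error is about 6–21% under an assumed ICC of 0.10–0.20 and 10 to 35 clinicians. It is higher only under full turnover, which the documents do not suggest. These figures rest on assumed inputs, an even split between periods, no covariates, and no clinician working in both groups. They illustrate the risk; they do not estimate this trial's error rate. For the match outcome, the direction of any error is unknown because the baseline match rate is unknown.

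**What to change.** 1. For the dose outcome, report standard errors clustered on the clinician who wrote the prescription, with a few-cluster correction, for example CR2 with Satterthwaite degrees of freedom. Section 10 already distinguishes the writer from the attending whose patient it is; one phrase would fix the unit.
2. Report the number of clinicians per group and period, and how many prescribe in both periods.
3. For the match outcome, report a risk difference from a linear probability model with the same correction, and show the four cell counts so that empty cells are visible.
4. State that clinician clustering does not cover shocks common to a whole site or period.

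**Cost.** SAP wording only, since the planned fixed effects already need prescriber identity. Intervals widen: in simulation A the CR2 interval was 1.02–1.15 times the ordinary width with stable clinicians, rising for doses to 1.08–1.86 times under full turnover. With 10 stable clinicians there are only about 7 degrees of freedom. The match outcome would be reported as a risk difference instead of an odds ratio.

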- Sample size: Based on historical UM data, we estimate that there will be 113 patients in the treatment group and 85 in the control group for the primary analysis (total 198). If 65% consent to complete the surveys, then there will be 74 and 55 patients in the treatment and control groups for the secondary analysis, respectively (total 129).

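### The plan names no model for binary outcomes; if logistic is used, any group-by-period cell without events leaves the difference-in-differences odds ratio with no finite estimate, and no fallback is given

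*Combined protocol and SAP*

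**What the plan says.** Section 10 (Statistical Considerations) gives one sentence on the main model: "We will fit linear or logistic regression models assessing outcomes as a function of an indicator of post-intervention status", a treatment-group indicator and the product of the two, adjusted for demographics and baseline comorbidities. Linear and logistic are both allowed. No outcome is assigned to either, no expected event rate is given, and there is no rule for separation or empty cells.

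Five of the six primary-analysis outcomes are proportions. One is concordance: "Proportion of patients in which the number of doses in the discharge opioid prescription equals the number of doses in the new default settings". The others are receipt of an opioid prescription at discharge, refills, office visits for pain, and emergency visits or admissions for pain. Many survey outcomes are also binary, including urgent-care and retail-clinic visits and two kinds of misuse.

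On the level of concordance before the change, Section 6 says of the pediatric orderset that "the default is currently 30 doses, consistent with the current departmental prescribing standard". It adds that a lower number will be chosen in September 2020. No dose distribution is given for the control prescribers. Section 1 cites one precedent, an adult emergency department study, in which prescriptions at the new default quantity rose from 20.6% to 43.3%.

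**The concern.** The period, group and interaction terms give each of the four cells its own level. In a logistic model, a cell with no events (or only events) drives its log odds to minus (or plus) infinity. The interaction is then infinite, or undefined if infinities cancel. Covariates do not cure this, because the cell indicator is still a combination of the model terms.

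The outcomes most exposed are the rare ones, and these are largely the balancing measures for which Section 10 hypothesises no change: utilisation for pain and misuse. Because two model families are open, an analyst who meets non-convergence could switch to the other for that outcome only. The choice would then depend on the data, and outcomes would be reported on a mixture of odds-ratio and percentage-point scales.

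**Working it through.** **The plan's own figures.** 113 + 85 = 198 for the primary analysis. At 65% consent, 0.65 × 113 = 73.45 (plan: 74), 0.65 × 85 = 55.25 (plan: 55) and 0.65 × 198 = 128.7 (plan: 129). These reproduce within rounding.

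**Cell sizes (assumed).** Section 6 says: "The pre-intervention period will start on October 1, 2019 and end September 30, 2020; the months of April and May 2020 will be excluded". That leaves 10 months before the change; October 2020 to July 2021 is 10 months after. If 113/85 and 74/55 cover both periods and split evenly, the cells are 57, 56, 43, 42 (primary) and 37, 37, 28, 27 (survey).

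**Chance of at least one empty cell** at a common event rate p (assumed): 1 − ∏[1 − (1 − p)^n].

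Example, primary at p = 5%: 0.95^57 = 0.054, 0.95^56 = 0.057, 0.95^43 = 0.110, 0.95^42 = 0.116, so 1 − 0.946 × 0.943 × 0.890 × 0.884 = 0.30.

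| p | Primary | Survey |
|---|---|---|
| 1% | 98% | 99% |
| 2% | 85% | 95% |
| 3% | 64% | 85% |
| 5% | 30% | 59% |
| 10% | 3% | 14% |

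The risk passes 50% below p = 3.7% (primary) and 5.7% (survey). It falls under 5% above about 8.8% and 13.2%. If 113/85 were instead the numbers per period, the primary risk would be 85% at 1%, 46% at 2% and 3% at 5%. If a planned subgroup halved the primary cells (28, 28, 21, 21), it would be about 75% at 5% and 29% at 10%.

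**Concordance.** The pre-period treatment cell and both control cells (57, 43, 42) are taken at one rate. The post-period treatment cell is ignored, since it is very unlikely to be empty if the default works.

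| Shared match rate | Risk of an empty cell |
|---|---|
| 1% | 95% |
| 2% | 77% |
| 5% | 26% |
| 10% | 2.5% |
| 20.6% | 0.01% |

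With both control cells at 20.6%, essentially only the pre-period treatment cell can be empty: 0.99^57 = 56% at a 1% match rate and 0.98^57 = 32% at 2%.

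**What the fits do** (illustrative counts; pre-treatment, post-treatment, pre-control, post-control):

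- 0/57, 34/56, 0/43, 1/42: logistic stops with a singular matrix. The linear model gives 34/56 − 0 − (1/42 − 0) = 0.607 − 0.024 = 0.583. Its HC3 standard error is the root of the sum of p(1 − p)n/(n − 1)² over cells: √(0.00442 + 0.00058) = 0.071.
- 0/56, 25/57, 1/42, 1/43: after 25 iterations the logistic interaction stands at 15.4 (SE 322), not converged. The linear model gives 0.439 (SE 0.074).
- 2/56, 25/57, 2/42, 2/43: logistic converges, 3.07 (SE 1.28).

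**An outcome that needs no assumed rate.** Section 4 removes from the primary analysis anyone not prescribed opioids after surgery, while Section 10 lists the share prescribed opioids at discharge as a primary-analysis outcome. If the two phrases mean the same prescription, that share is 100% in all four cells. No logistic fit exists, and a linear fit returns zero with no variance.

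**The case against.** A reader might infer that the logistic models will often fail, that concordance is the clearest case because three of its four cells should be near zero, and that most refill, visit and misuse outcomes would be left without a usable estimate. The documents do not support any of these.

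- Section 10 already permits a linear model, which stays estimable. Logistic for binary outcomes is the natural reading, but it is not written.
- No event rate is given for any binary outcome, and several (pain well controlled, pain resolved by day 14, leftover doses) have no evident reason to be rare.
- For concordance, the 30-dose default supports a low match rate in the pre-period treatment cell. It says nothing firm about controls: their dose distribution is absent, their use of the pediatric orderset is left open in Section 6, and the new default is not yet chosen. At the one cited precedent, 20.6%, the problem disappears, although that study concerned adult emergency prescribing.
- Concordance is not the clearest case; the discharge-prescription outcome is, on the reading given above.
- Only the maximum-likelihood odds ratio is lost. Risk-difference, exact and penalised analyses remain, and the dose-count outcome is untouched.

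These objections limit the claim but do not remove it. The plan still leaves the model open and names no fallback.

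**Conclusion.** The point holds as a conditional one. The defect is an unassigned model and a missing rule for sparse cells, not a predicted failure. If logistic regression is used, an empty cell is more likely than not for primary outcomes with event rates below about 3.7% and survey outcomes below about 5.7%. It is a minor risk at 10% or more in the primary set, and at about 13% or more in the survey set. This rests on a common rate across cells, an even split, and sample sizes that cover both periods. The survey cells could be smaller still, since Section 4 also requires completed baseline and day-14 surveys.

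Whether pain-related emergency visits, retail-clinic visits or misuse are that rare cannot be settled from the documents. For concordance the risk is anywhere from near zero to about 95%, with 32% to 56% if only the pre-period treatment cell is low (1–2%) and controls match the precedent. The discharge-prescription outcome cannot be analysed in the stated set if the Section 4 exclusion refers to the discharge prescription.

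**What to change.** State in Section 10 that every binary outcome is analysed with the linear probability difference-in-differences model, reported as a percentage-point difference with robust standard errors (HC3, for example). Name Firth-penalised logistic regression as a check for outcomes with sparse cells. Say that this choice does not depend on whether an ordinary logistic model converges.

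Separately, reconcile the Section 4 exclusion with the discharge-prescription outcome, either by giving that outcome a denominator that includes patients without a prescription or by removing it from the list.

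The cost is SAP wording; no data collection changes. The linear model has a small downside: fitted values can fall outside 0 to 1, and robust errors are approximate in very sparse cells (zero if no event occurs anywhere, so such outcomes should be reported as counts only). In simulations with no effect and event rates of 1% to 10%, the HC3 test rejected about 5% of the time or less, and was conservative at the lowest rates.
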